6.3 Statistical analysis of technical success

The ideal outcome, from a technical standpoint, is complete removal of the tumor and absence of cancer in an area of 3 mm beyond the region where the tumor appeared on the interventional contrast CT image (the “ablative margin”). In the past, **such an outcome was rare with only 3 successful cases out of 110** (see Kim, et al., 2010). However, it is notable that in previous work [5] the tumor was found to recur in 0/15, 2/34 (5.9%), 10/53 (18.9%), and 25/110 (22.7%) cases when the attained ablative margin was $\geq 3\text{mm}$, $\geq 2\text{mm}$, $\geq 1\text{mm}$, and $\geq 0\text{mm}$, respectively. Therefore, it is reasonable to expect that attainment of an ablative margin of $\geq 3\text{mm}$ would be a very successful outcome, and we will analyze this event as a secondary outcome.

The dependent variable in the primary analysis of technical success is the binary indicator of whether or not the RFA-GP surgery resulted in an ablative margin of $\geq 3\text{ mm}$. Let p_{RFA} denote the true proportion of times an ablative margin of $\geq 3\text{ mm}$ is obtained in the proposed PGP study. As a benchmark against which to compare p_{RFA} , we deliberately err on the side of over-estimating the success of the standard procedure by using $p_{\text{base}} = \frac{3}{110} + \frac{z_{0.975}}{110} \left(\frac{3(110-3)}{110} \right)^{1/2} = 0.0577$, where $z_{0.975}$ is the 97.5'th quantile of the standard normal distribution, as the benchmark. Note that p_{base} is the upper end-point of an approximate 95% confidence interval for the true proportion of times an ablative margin of $\geq 3\text{ mm}$ is obtained in the absence of PGP in [5]. We will test the one-sided hypothesis:

$$H_0: p_{\text{RFA}} \leq p_{\text{base}} \text{ against the alternative } H_1: p_{\text{RFA}} > p_{\text{base}}$$

using a one-sample test of proportions.

Because technical success will be assessed by each of three raters, the hypothesis test given above can be tested in a manner that allows for the effects of each rater and the clustering of ratings by subject to be accounted. Let TS_{ij} denote the technical success rating of subject i by rater j . We may then estimate the Rasch model

$$TS_{ij} \mid \theta_i \sim \text{Bern}(p_{ij})$$

where

$$p_{ij} = \Pr(TS_{ij} = 1 \mid \theta_i) = \frac{\exp(\theta_i + \beta_j)}{1 + \exp(\theta_i + \beta_j)}$$

and $\theta_i \sim \text{normal}(\theta_{\text{RFA}}, \sigma^2)$ describes the distribution of the log-odds of technical success across the population of subjects, accounting for the clustering of ratings by subjects, and $\beta_1 + \beta_2 + \beta_3 = 0$ is an identifiability constraint. Note that we use this identifiability constraint in lieu of treating $\beta_1, \beta_2, \beta_3$ as random-effect parameters, which is not advisable with only three raters. The target of inference is θ_{RFA} , the population mean log-odds of success, and the comparison value is

$$\theta_{base} = \log\left(\frac{p_{base}}{1 - p_{base}}\right)$$

Therefore, with data from multiple raters, we may transform the above hypothesis test to:

$$H_0: \theta_{RFA} \leq \theta_{base} \text{ against the alternative } H_1: \theta_{RFA} > \theta_{base}$$

or define

$$p_{RFA} = \frac{\exp(\theta_i)}{1 + \exp(\theta_i)}$$

and test $H_0: p_{RFA} \leq p_{base}$ against the alternative $H_1: p_{RFA} > p_{base}$. The former is preferred as the parameters are unrestricted. In addition to reporting p-values, we will also report the estimated probability for the proportion of occasions that an ablative margin of $\geq 3\text{mm}$ was obtained and an associated 95% confidence interval for p_{RFA} both in the full sample and for each tumor size subgroup.

We realize that the comparison to a fixed literature-based historical control value is non-ideal. Ideally, individual patient data from multiple historical studies performed in the absence of PGP that can be analyzed simultaneously with the data from the new study. This would allow us to account for study-to-study variability and to test the hypothesis that PGP results in a higher probability of technical success. If patient characteristics and baseline clinical information was available across the studies we could also adjust for such factors to make the studies more homogeneous. In lieu of having such data, we err on the side of conservatism by making the comparison point the upper limit of a 95% confidence interval based on the non-PGP study result, a threshold for success that is almost certainly more demanding than if we had the just described data and performed a statistical test for a two-population comparison. What we are essentially proposing to do is to reject the null hypothesis that the lower 95% confidence interval in the PGP study exceeds the upper 95% limit in the non-PGP study. Note that the non-overlap of two confidence intervals for two groups implies that a hypothesis test will reject the null hypothesis of no difference between the groups. Therefore, if we reject the null hypothesis in the proposal of the probability under PGP being less than or equal to θ_{base} , or to p_{base} , we can be very confident that PGP has a higher probability of technical success.

Finally, to evaluate the relationship between tumor size and the likelihood of obtaining an ablative margin $\geq 3\text{mm}$, we will estimate a logistic regression model in which tumor size is a lone predictor. That is, we will estimate the value of $\beta = (\beta_0, \beta_{size})$ in the model:

$$\Pr(\text{Ablative margin} \geq 3\text{mm} \mid \text{size}) = \frac{\exp(\beta_0 + \beta_1 \text{size})}{1 + \exp(\beta_0 + \beta_1 \text{size})}$$

so that the probability of technical success when PGP is used is able to be predicted for a patient with a given exact tumor size. This expression will be helpful if it is necessary to determine the expected technical success for the size distribution of a sample of patients analyzed in a prior study. In the meantime, the fitted logistic regression model will only be used as a means of graphically summarizing the results with respect to tumor size.

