6.3.1 Power for technical success

If the analysis of the above one-sided hypothesis test for p_{RFA} for an ablative margin of 3mm is conducted using Fisher's exact test, then with a sample-size of 62 lesions and allowing a type I error of 0.05, we can detect a value of $p_{RFA} > 0.161$ with 80% power. That is, the minimal detectable p_{RFA} difference is 0.103. Subgroup analyses (e.g., based on treated tumor size) will require larger effect sizes to retain the same level of power. However, the study is only intended to be powered for the primary analysis.

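### The technical-success benchmark is built from 3/110, but the same paragraph of the SAP implies that 15 of those 110 historical cases reached the 3 mm margin

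*SAP*

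**What the plan says.** SAP section 6.3 opens with an ideal outcome (tumor removed, plus 3 mm beyond it free of cancer) and says of past practice that "such an outcome was rare with only 3 successful cases out of 110". Still citing reference [5], it then reports that "the tumor was found to recur in 0/15, 2/34 (5.9%), 10/53 (18.9%), and 25/110 (22.7%) cases when the attained ablative margin was" at least 3, 2, 1 and 0 mm, respectively.

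The endpoint follows, with its threshold set at 3 mm or more: "The dependent variable in the primary analysis of technical success is the binary indicator of whether or not the RFA-GP surgery resulted in an ablative" (the sentence goes on to name that threshold). For the benchmark the SAP says "we deliberately err on the side of over-estimating the success of the standard procedure by using" p_base = 0.0577, computed from 3/110. It says that this value "is the upper end-point of an approximate 95% confidence interval for the true proportion of times an ablative margin of" at least 3 mm without PGP in reference [5]. The test is one-sided, "using a one-sample test of proportions".

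Section 6.3.1 gives the power for 62 lesions at type I error 0.05: 80% at p_RFA = 0.161, so that "the minimal detectable p_{RFA} difference is 0.103".

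**The concern.** The thresholds in the recurrence series are cumulative, and the last denominator is the same 110 cases. The first denominator should therefore be the number of historical cases with a margin of at least 3 mm. That number is 15, five times the 3 used for the benchmark. The tested event and the description of p_base both refer to the category whose denominator is 15.

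This threshold decides one of the trial's two primary outcomes, and technical success is also the protocol's primary objective. A single-arm design has no concurrent control to expose a wrong benchmark. The SAP defends its fixed historical control on the ground that the benchmark is set deliberately high, so that rejection would be strong evidence of superiority. If the historical rate is 13.6%, the benchmark is less than half of it (0.0577/0.1364 = 0.42), and that defence reverses. The Rasch analysis is affected in the same way, because theta_base is the logit of p_base.

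**Working it through.** **Inputs.** From SAP 6.3: 3/110, the denominators 15, 34, 53 and 110, and the formula for p_base. From SAP 6.1 and 6.3.1: 62 lesions, one-sided alpha 0.05, 80% power. Lesions are treated as independent, as in the SAP's power section.

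**1. The SAP's own figures.** The formula is p_base = x/110 + (1.96/110) × √[x(110 − x)/110].

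- With x = 3: 0.0273 + 0.0178 × √2.918 = 0.0577, as stated.
- Exact one-sample binomial, n = 62, p0 = 0.0577: P(X ≥ 7) = 0.066 and P(X ≥ 8) = 0.026, so the test rejects at 8 or more.
- P(X ≥ 8) reaches 0.80 at p = 0.1607, a difference of 0.103. Both figures in section 6.3.1 reproduce.

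The arithmetic is therefore sound, and only the input 3/110 is in question.

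**2. Reading the recurrence series.** The groups cannot be disjoint, since 15 + 34 + 53 + 110 = 212 exceeds 110. They are nested, which gives 15/110 = 0.136 for at least 3 mm (Wald 95% interval 0.072 to 0.200; exact 0.078 to 0.215). Both intervals lie wholly above 0.0577. Counting only recurrence-free cases changes nothing, because recurrence in that group was 0/15.

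**3. The current rule if 15/110 is right.**

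- The smallest success is 8/62 = 12.9%, below 13.6%.
- If PGP only matches history, P(X ≥ 8 | 0.1364) = 0.62.
- With the historical rate at the ends of the Wald interval, this is 0.08 (at 0.072) and 0.95 (at 0.200).
- A large-sample z test rejects at 7 or more, and the probability at 0.1364 is then 0.76.
- A one-sided two-sample Fisher test of 8/62 gives p = 0.012 against 3/110 and p = 0.64 against 15/110.

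**4. The rule recomputed (n = 62, one-sided 0.05, exact).**

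| Benchmark | p0 | Cut-off | Detectable p_RFA, 80% power | Power at 0.161 |
|---|---|---|---|---|
| As written, 3/110, upper Wald limit | 0.0577 | 8 | 0.161 | 80% |
| 15/110, point estimate | 0.1364 | 14 | 0.265 | 11.5% |
| 15/110, SAP formula | 0.2005 | 19 | 0.350 | 0.3% |
| 15/110, exact upper limit | 0.215 | 20 | 0.366 | 0.1% |

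The third row is 0.1364 + 0.0178 × √(15 × 95/110) = 0.2005. On the logit scale, theta_base moves from ln(0.0577/0.9423) = −2.79 to ln(0.2005/0.7995) = −1.38.

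**The case against.** The SAP nowhere states that 15 cases succeeded. The figure is read from the denominator of a recurrence fraction, and reference [5] is not available here. The 3 could belong to a stricter margin, or to the composite ideal outcome at the start of section 6.3, with the 15 classified in some other way. The remedy might then be an explanation rather than a new number. The same paragraph also calls the 3 mm event a secondary outcome before making it the primary dependent variable, so the text may have merged two definitions. This uncertainty stands, and the consequences above are conditional on 15/110. It does not rescue the text: if 3/110 describes another event, the null value does not match the stated dependent variable.

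The 0.62 is one point in a wide range, and it depends on the exact test, which section 6.3.1 introduces only conditionally. That is fair. However, the probability exceeds 0.05 across the whole Wald interval, and the z-test rule makes it larger at 13.6%.

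Against the null as written, the test has size 0.026 and the stated power is correct. That is also true. The fault is that the null may not describe historical practice.

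Section 6.3 concedes that a fixed historical control is not ideal, but it does not address 3 versus 15.

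**Conclusion.** The concern holds. Section 6.3 gives two incompatible counts for one event in one historical series, and it builds the decision threshold on the lower one. The conflict itself rests only on the SAP's text. Its consequences assume that the series is nested, as the thresholds and the final 110 indicate, and that the 62 lesions are independent. On those assumptions:

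- The trial could claim superiority with a result numerically below its own historical rate.
- The chance of a false claim at 13.6% is 0.62, against a nominal 0.05.
- The effect detectable with 80% power under the SAP's benchmark rule is 0.35, not 0.161.

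This must be corrected before the technical-success analysis is run.

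**What to change.** Check reference [5] to establish which event the 3 and the 15 each describe, and record the answer in section 6.3. Then:

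- **If 15/110 is the count for at least 3 mm:** keep the endpoint, and recompute p_base (0.2005 by the SAP's formula, 0.215 by the exact limit) and theta_base. Restate section 6.3.1 with a cut-off of 19 or 20 of 62 and a detectable p_RFA of 0.35 to 0.37.
- **If 3/110 belongs to a different event:** state that definition, explain why it differs from the 15, and make the dependent variable and the benchmark refer to the same event.

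In either case, say once whether the 3 mm margin is the primary or a secondary outcome. As a lesser point, a Wald limit is poor with 3 events. The exact upper limit for 3/110 is 0.078 rather than 0.058, which would move the cut-off from 8 to 9.

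The direct cost is one source check, one recalculation and revised wording, with no new procedures. If 15/110 is confirmed, the claim of sufficient power in section 6.1 must also be justified again. Either a true rate of about 0.35 is a realistic expectation for PGP, or the SAP should say that 62 lesions are too few for smaller gains.

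### The technical-success benchmark of 0.0577 is a Wald limit from 3 events in 110 and is less conservative than the 95% upper limit it is described as; Wilson and exact limits are about 0.077

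*SAP*

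**What the plan says.** SAP section 6.3 takes its technical benchmark from one historical series, in which "such an outcome was rare with only 3 successful cases out of 110". It sets p_base = 0.0577 by adding to 3/110 a multiple of the usual large-sample standard error; the multiplier "is the 97.5'th quantile of the standard normal distribution". It states that the result "is the upper end-point of an approximate 95% confidence interval" for the rate without the platform. The purpose is given as "we deliberately err on the side of over-estimating the success of the standard procedure".

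The null hypothesis is p_RFA ≤ p_base, tested one-sided. The same value, on the logit scale, is the comparison value theta_base for the three-rater Rasch model.

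Later in section 6.3 the SAP defends the use of a fixed historical value. There the limit is described as a 95% limit without the qualifier that it is approximate, and is called "a threshold for success that is almost certainly more demanding than if we had the just described data" (individual patient data from several historical studies).

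Section 6.3.1 gives power on the assumption that an exact test is used. With 62 lesions and a type I error of 0.05, it states 80% power for a rate above 0.161, a detectable difference of 0.103.

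**The concern.** The benchmark is the null value for one of the trial's two primary outcomes. In a single-arm trial with a literature control, the distance between that value and the observed 2.7% is the only allowance for sampling error in the control. The SAP's argument for the design depends on that allowance being a genuine 95% limit.

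With 3 events the Wald formula does not deliver one. The binomial distribution is strongly skewed at this count, and a symmetric interval puts its upper end too low. The null value is then lower than the SAP's description implies. A result that just passes would be reported as clearing a 95% upper limit of standard performance when it clears a weaker one.

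**Working it through.** **Inputs.** Historical count 3/110, quantile 1.96 and p_base = 0.0577 (SAP 6.3); 62 lesions, one-sided alpha 0.05, 80% power, detectable rate 0.161 and difference 0.103 (SAP 6.3.1). Lesions are treated as independent, as section 6.3.1 does. That section names Fisher's exact test; for one sample against a fixed value, the exact test is the binomial test.

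**Step 1: reproduce the benchmark.**
- p = 3/110 = 0.02727.
- Standard error = sqrt(0.02727 × 0.97273 / 110) = 0.01553.
- Upper limit = 0.02727 + 1.96 × 0.01553 = 0.0577, which matches the SAP.
- Lower limit = 0.02727 − 1.96 × 0.01553 = −0.0032, which is impossible for a proportion.

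**Step 2: reproduce the power statement.**
- P(X ≥ 7 | 62, 0.0577) = 0.066 and P(X ≥ 8 | 62, 0.0577) = 0.026, so the smallest count with a tail of at most 0.05 is 8.
- P(X ≥ 8 | 62, p) = 0.80 at p = 0.1607. The difference is 0.1607 − 0.0577 = 0.1030. Both published figures match.

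**Step 3: what level 0.0577 really has.** A two-sided 95% exact upper limit is the p at which P(X ≤ 3 | 110, p) = 0.025. At p = 0.0577 that probability is about 0.1155. So 0.0577 is about an 88% one-sided limit (1 − 0.1155), not a 97.5% one.

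**Step 4: other upper limits for 3/110.**

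| Method | Upper limit |
|---|---|
| Wald (SAP) | 0.0577 |
| Jeffreys | 0.0710 |
| Mid-P | 0.0724 |
| Wilson | 0.0771 |
| Clopper-Pearson | 0.0776 |
| Agresti-Coull | 0.0815 |

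Even the one-sided 95% limits are above 0.0577: Wilson 0.0663, exact 0.0690.

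**Step 5: consequence if 3/110 stands.**

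| p_base | Critical count of 62 | Actual alpha | Rate with 80% power | Difference | Power at 0.161 |
|---|---|---|---|---|---|
| 0.0577 | 8 | 0.026 | 0.1607 | 0.103 | 80.2% |
| 0.0771 | 9 | 0.048 | 0.1785 | 0.101 | 68.5% |
| 0.0776 | 9 | 0.049 | 0.1785 | 0.101 | 68.5% |

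The comparison value theta_base moves from ln(0.0577/0.9423) = −2.79 to ln(0.0771/0.9229) = −2.48.

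Section 6.3 also explains the test as requiring the trial's lower limit to exceed the historical upper limit. The exact one-sided 95% lower limit for 8/62 is 0.0659, which clears 0.0577 but not 0.077. For 9/62 it is 0.0779, which clears both.

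**Step 6: consequence if the count is 15/110.** The recurrence figures in section 6.3 run through cumulative margin groups, from 0/15 at 3 mm or more to 25/110 at 0 mm or more. They imply that 15 of the 110 reached 3 mm, not 3. With 15/110 = 0.1364:

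| Method | p_base | Critical count of 62 | Rate with 80% power |
|---|---|---|---|
| Wald | 0.200 | 19 | 0.350 |
| Clopper-Pearson | 0.215 | 20 | 0.366 |

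The gap between methods is 0.0776/0.0577 − 1 = 34% at 3 events and 0.215/0.200 − 1, about 7%, at 15 events.

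**The case against.** The SAP prints its formula, names the quantile and, where it defines the limit, calls the interval approximate. This stands: 0.0577 is computed correctly and the issue is the choice of method. But the approximation is off by about a third, and the later defence of the threshold drops the qualifier.

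A reader might infer that the detectable rate in section 6.3.1 is wrong. It is not: 0.161 and 0.103 follow exactly from p_base = 0.0577, and change only if the benchmark changes.

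A reader might also infer that the benchmark is too easy, or that the SAP's statement "a threshold for success that is almost certainly more demanding" is false. The documents do not support either reading. The value is about twice the observed 2.7%. If the true standard rate were 3/110, the chance of 8 or more successes in 62 would be about 0.0003. A one-sided two-sample Fisher test against 3/110 already rejects at 7/62 (p = 0.027), whereas the p_base rule needs 8/62 (Fisher p = 0.012), so the rule is stricter than that simple comparison. The comparison that the SAP has in mind, with several historical studies, cannot be checked here. The false-positive rate of the 8/62 rule does reach 10.6% if the true standard rate is 0.0776, but that is a worst case; at the SAP's own null it is 2.6%.

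Two further points stand. The SAP states no critical count, and its main analysis may be the Rasch model, so 8 and 9 of 62 only illustrate the exact test assumed for power. And the conflict between 3/110 and the 15 cases at 3 mm is the larger problem and comes first.

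**Conclusion.** The point holds as one about interval method. The null value for technical success is described as a 95% upper limit but has roughly the level of an 88% one-sided exact limit; standard 95% methods give about 0.077. The benchmark is less conservative than section 6.3 says, though still above the observed rate.

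The practical effect is modest if 3/110 is right: one more success under an exact test, and a detectable rate 0.018 higher (0.1785 − 0.1607), with almost no change in the detectable difference. A result of exactly 8/62 would pass against the present benchmark and fail against a Wilson or exact one. If 15/110 is right, the choice of method matters less, and the change of numerator dominates.

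These figures assume 62 independent lesions, one binary outcome per lesion and one-sided alpha 0.05.

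**What to change.** First reconcile, in SAP section 6.3, the 3/110 count with the 15 cases at a margin of 3 mm or more. Then compute p_base as a Wilson or Clopper-Pearson upper limit of the reconciled count, name the method, and derive theta_base from it. Restate section 6.3.1 to match:

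- If 3/110 stands: p_base about 0.077, detectable rate 0.1785, difference about 0.101, power at 0.161 about 68.5%.
- If 15/110 applies: p_base 0.215 by Clopper-Pearson, detectable rate about 0.366.

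A critical count need not be written in unless the exact test is made the primary analysis. If the sponsor prefers to keep 0.0577, the text should present it as a chosen fixed benchmark and drop the description of it as a 95% limit.

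The cost is one formula, one derived value and one power paragraph. With 3/110 the stated detectable rate becomes slightly less favourable.

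### The three-rater Rasch test of technical success compares the median subject's log-odds with the logit of a population proportion, so it does not test the stated hypothesis

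*SAP*

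**What the plan says.** SAP section 6.3 defines p_RFA as the true proportion of ablations that reach a margin of at least 3 mm. The benchmark p_base = 0.0577 is the upper 95% confidence limit for a historical 3 out of 110. The one-sided hypothesis p_RFA > p_base is to be tested "using a one-sample test of proportions".

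The section then notes that three raters will assess each case, so that "the hypothesis test given above can be tested in a manner that allows for the effects of each rater". Within-subject correlation is to be handled too. The wording is permissive: "We may then estimate the Rasch model". In that model the subject effects theta_i are normal with mean theta_RFA and variance sigma², and three fixed rater effects sum to zero. The inferential target is theta_RFA, described as "the population mean log-odds of success, and the comparison value is" theta_base = logit(p_base).

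The link between the two tests is stated as an equivalence: "Therefore, with data from multiple raters, we may transform the above hypothesis test to" one on theta_RFA against theta_base. A second form defines p_RFA as the inverse logit of theta_i. The SAP prefers the theta form of the two.

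Later in 6.3 the two thresholds are treated as interchangeable: "if we reject the null hypothesis in the proposal of the probability under PGP being less than or equal to" theta_base, or p_base, the reader may be very confident in PGP. Section 6.3.1 gives 80% power at p_RFA = 0.161 for an exact test with 62 lesions.

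**The concern.** The benchmark is a proportion across a population of cases. The Rasch target is the centre of a distribution of subject-level log-odds. The inverse logit is non-linear, so averaging and transforming cannot be swapped. When success is rare, the population proportion is larger than the inverse logit of the mean log-odds whenever subjects differ. Nothing in 6.3 integrates over sigma² or moves p_base to the subject-specific scale.

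The second form does not repair this. As printed, the inverse logit of theta_i is a different random quantity for each subject. If theta_i is a slip for theta_RFA, the result is again the median subject's probability.

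Section 6.2 lists technical success as one of two primary outcomes, and the Rasch model is the only method the SAP gives for handling three ratings per case. An analyst who uses it as written tests a harder hypothesis than the one stated and could report that a device meeting its design target failed to beat the benchmark. The SAP also promises an estimate: "we will also report the estimated probability for the proportion of occasions that an ablative margin of" at least 3 mm was reached. If that figure is taken from the printed back-transform it will be too low. A raw or integrated proportion would not be.

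**Working it through.** **Inputs from the SAP.** Historical 3/110, p_base = 0.0577 and three raters (6.3); 62 lesions, one-sided alpha 0.05 and design alternative 0.161 (6.3.1). Sigma and rater agreement are not given, so sigma is assumed to be 0.5, 1, 2 or 3.

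**1. The plan's own figures reproduce.**
- p_base = 3/110 + (1.96/110)·√(3·107/110) = 0.0577.
- theta_base = log(0.0577/0.9423) = −2.793.
- Exact one-sample binomial, n = 62: a cut-off of 7 successes has size 0.066, so the test rejects at 8 or more. Its size is 0.026 and its power at 0.161 is 0.802, which matches the stated 80%.

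**2. What the Rasch target means.** With equal raters, the population proportion is

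m(theta, sigma) = E[expit(theta + sigma·Z)], Z ~ N(0, 1), where expit is the inverse logit.

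This was evaluated by Gauss-Hermite quadrature. The model-implied pairwise kappa is (E[p²] − m²)/(m(1 − m)), where p = expit(theta + sigma·Z).

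| Assumed sigma | theta_RFA giving a true 16.1% | expit(theta_RFA) | Pairwise kappa | Population proportion when theta_RFA = theta_base |
|---|---|---|---|---|
| 0.5 | −1.73 | 15.0% | 0.03 | 6.4% |
| 1 | −1.95 | 12.4% | 0.12 | 8.3% |
| 2 | −2.63 | 6.7% | 0.33 | about 14.6% |
| 3 | −3.45 | 3.1% | 0.48 | 21.1% |

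The last column is the effective benchmark on the proportion scale; the plan intends 5.77%. It reaches 16.1% at sigma = 2.21 (kappa about 0.37). For larger sigma, the design alternative lies inside the Rasch null. A kappa of 0.6 at 16.1% would imply sigma of about 4.1, where expit(theta_RFA) is about 1%.

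**3. Rater effects add to it.** With sigma = 0 but rater effects of (−1, 0, 1), the rater-averaged proportion at theta_base is 0.074, not 0.0577. Sigma = 0 is therefore necessary for equivalence but not sufficient.

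**4. Test behaviour by simulation.** Assumptions: 62 independent lesions, three equal raters, ratings independent given theta_i, and a maximum-likelihood fit. The statistic is a signed likelihood-ratio test at 1.645, which is a choice made here because the SAP names none. Several runs of 300 to 1,000 trials per setting gave the Rasch ranges below. The marginal test uses the integrated probability against 0.0577 and comes from one run of 400 trials on the same data and fit as one of the Rasch runs.

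| Assumed sigma | Rasch power at 16.1% | Marginal-test power at 16.1% |
|---|---|---|
| 0.5 | 0.79–0.87 | 1.00 |
| 1 | 0.57–0.66 | 0.99 |
| 2 | 0.06–0.13 | 0.98 |
| 3 | 0.00–0.01 | 0.96 |

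At a true 5.77%, the Rasch theta test rejects in at most 1% of trials and the marginal test in 5–6%. The mismatch therefore makes the test conservative.

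**The case against.** **The Rasch analysis is optional.** The SAP says it will run the one-sample test and only may fit the Rasch model. The stated preference for the theta form ranks the two Rasch versions, not Rasch above the one-sample test. This is right and limits the reach: if the one-sample test is run, nothing here changes it. However, the SAP as supplied has no consensus, majority or designated-reader rule to turn three ratings into one verdict per lesion, which leads the analyst to the Rasch model. The protocol refers to sections of a separate clinical protocol on outcomes and procedures that are not supplied; such a rule may be there.

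**The error is conservative and the target is named openly.** Both are true, and rejection by the Rasch test would still support PGP. What fails is the claim of equivalence, and with it the meaning of a non-rejection. The conservatism that 6.3 announces is the use of a confidence limit as the benchmark. This second penalty is undisclosed and grows with sigma, that is, as raters agree more closely.

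**The power figures are soft.** This stands. Repeat simulations differ by more than Monte Carlo error at sigma 1, and the values depend on an unnamed statistic and on fitting details, hence the ranges. The marginal test's near-full power comes from pooling 186 ratings (62 × 3) treated as independent given the subject, so it is not a like-for-like match to the planned 80%. That 80% in turn holds only if the single verdict per lesion succeeds 16.1% of the time. Under a majority read with a per-rating rate of 16.1%, the majority verdict succeeds in 12.6% of lesions at sigma 2 and 14.1% at sigma 3. The exact test then has power of about 0.53 and 0.66.

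**Section 6.3.1 already ties its power to an exact test.** Largely so: the sentence is conditional on that test, "then with a sample-size of 62 lesions and allowing a type I error of 0.05, we can detect a value of" 0.161. A further statement would be a small clarification.

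**Conclusion.** The concern holds. The Rasch hypothesis on theta_RFA is not a transform of the hypothesis on p_RFA unless subjects do not vary and the raters do not differ. Neither printed Rasch form tests the stated proportion.

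Its size depends on sigma, which the documents do not give. At the design alternative, the loss is minor only when raters agree little better than chance (sigma 0.5, kappa 0.03). It is substantial at sigma 1, close to total at sigma 2, and beyond sigma of about 2.2 the tested null is true. These figures assume independent lesions, equal raters, conditionally independent ratings and a likelihood-ratio test. Two lesions in one patient would lower the power of both tests somewhat.

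The committed one-sample test, its benchmark and its 80% power figure are not affected, and no inflation of false positives arises. The point should be fixed before analysis, because it concerns a primary outcome and the only multi-rater method in the SAP.

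**What to change.** For the multi-rater analysis, make the marginal probability of success the target, and test and report it against p_base = 0.0577. Either route works:

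- Keep the Rasch fit, integrate expit(theta + beta_j) over the fitted N(theta_RFA, sigma²) and average over the three raters. Give a delta-method interval or a bootstrap interval that resamples patients.
- Fit a population-averaged (GEE) model with rater effects and a robust variance clustered by patient.

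Delete the test of theta_RFA against logit(p_base) and the definition of p_RFA as the inverse logit of theta_i. Amend the later text in 6.3 that treats theta_base and p_base as equivalent thresholds. Say plainly in 6.3.1 that the 80% power refers to the one-sample exact test only.

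The cost is SAP wording and a few lines of code. No extra data, raters or patients are needed.
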